11.4 Recording of Data

An eCRF is required and must be completed for each subject by qualified and authorized personnel. All data on the eCRF must reflect the corresponding source document, except when a section of the eCRF itself is used as the source document. Any correction to entries made on the eCRF must be documented in a valid audit trail where the correction is dated, the individual making the correction is identified, the reason for the change is stated, and the original data are not obscured. Only data required by the protocol for the purposes of the study should be collected.

The investigator must sign each eCRF. The investigator will report the eCRFs to the sponsor and retain a copy of the eCRFs.

11.5 Identification of Source Data

All data to be recorded on the eCRF must reflect the corresponding source documents.

11.6 Retention of Records

The circumstances of completion or termination of the study notwithstanding, the investigator (or if regionally required, the head of the medical institution or the designated representative) is responsible for retaining all study documents, including but not limited to the protocol, copies of eCRFs, the Investigator's Brochure, and regulatory agency registration documents (eg, Form FDA 1572, ICFs, and IRB/IEC correspondence). The site should plan to retain study documents, as directed by the sponsor, for at least 2 years after the last approval of a marketing application in an ICH region and until there are no pending or contemplated marketing applications in an ICH region or at least 3 years have elapsed since the formal discontinuation of clinical development of the investigational product.

It is requested that at the completion of the required retention period, or should the investigator retire or relocate, the investigator contact the sponsor, allowing the sponsor the option of permanently retaining the study records.

11.7 Auditing Procedures and Inspection

In addition to routine monitoring procedures, the sponsor's Clinical Quality Assurance department conducts audits of clinical research activities in accordance with the sponsor's standard operating procedures to evaluate compliance with the principles of ICH GCP and all applicable local regulations. If a government regulatory authority requests an inspection during the study or after its completion, the investigator must inform the sponsor immediately.

11.8 Handling of Study Drug

All study drug will be supplied to the principal investigator (or a designated pharmacist) by the sponsor. Drug supplies must be kept in an appropriate secure area (eg, locked cabinet) and stored according to the conditions specified on the drug labels. The investigator (or a designated pharmacist) must maintain an accurate record of the shipment and dispensing of the study drug in a drug accountability ledger, a copy of which must be given to the sponsor at the end of the study. An accurate record of the date and amount of study drug dispensed to each subject must be available for inspection at any time. The CRA will visit the site and review these documents along with all other study conduct documents at appropriate intervals once study drug has been received by the site.

All drug supplies are to be used only for this study and not for any other purpose. The investigator (or site personnel) must not destroy any drug labels or any partly used or unused drug supply before approval to do so by the sponsor. At the conclusion of the study and as appropriate during the study, the investigator (or a designated pharmacist) will return all used and unused drug containers, drug labels, and a copy of the completed drug disposition form to the sponsor's CRA (or designated contractor).

11.9 Publication of Results

All manuscripts, abstracts, or other modes of presentation arising from the results of the study must be reviewed and approved in writing by the sponsor in advance of submission pursuant to the terms and conditions set forth in the executed CTA between the sponsor/CRO and the institution/investigator. The review is aimed at protecting the sponsor's proprietary information existing either at the date of the commencement of the study or generated during the study. The detailed obligations regarding the publication of any data, material results, or other information generated or created in relation to the study shall be set out in the agreement between each investigator and the sponsor or CRO, as appropriate.

11.10 Disclosure and Confidentiality

The contents of this protocol and any amendments and results obtained during the study should be kept confidential by the investigator, the investigator's staff, and the IRB/IEC and will not be disclosed in whole or in part to others, or used for any purpose other than reviewing or performing the study, without the written consent of the sponsor. No data collected as part of this study will be used in any written work, including publications, without the written consent of the sponsor. These obligations of confidentiality and non-use shall in no way diminish such obligations as set forth in either the Confidentiality Agreement or CTA executed between the sponsor/CRO and the institution/investigator. All persons assisting in the performance of this study must be bound by the obligations of confidentiality and non-use set forth in either the Confidentiality Agreement or CTA executed between the institution/investigator and the sponsor/CRO.

11.11 Discontinuation of Study

The sponsor reserves the right to discontinue the study for medical reasons or any other reason at any time. If a study is prematurely terminated or suspended, the sponsor will promptly inform the investigators/institutions and regulatory authorities of the termination or suspension and the reason(s) for the termination or suspension. The IRB/IEC will also be informed promptly and provided the reason(s) for the termination or suspension by the sponsor or by the investigator/institution, as specified by the applicable regulatory requirement(s).

The investigator reserves the right to discontinue the study should his/her judgment so dictate. If the investigator terminates or suspends a study without prior agreement of the sponsor, the investigator should inform the institution where applicable, and the investigator/institution should promptly inform the sponsor and the IRB/IEC and provide the sponsor and the IRB/IEC with a detailed written explanation of the termination or suspension. Study records must be retained as noted above.

11.12 Subject Insurance and Indemnity

The sponsor will provide insurance for any subjects participating in the study in accordance with all applicable laws and regulations.

12 APPENDICES

Appendix 1 Sponsor's Grading for Laboratory Values

(revised per Amendment 01)

| | Grade 1 | Grade 2 | Grade 3 | Grade 4 |
|--|---|---|---|---|
| BLOOD/BONE MARROW | | | | |
| Hemoglobin (conversion from g/dL×0.6206) | Female (ULN=15.9 g/dL) <11.1 – 10.0 g/dL <111 – 100 g/L <6.9 – 6.2 mmol/L Male (ULN=17.7 g/dL) <12.6 – 10.0 g/dL <126 – 100 g/L <7.8 – 6.2 mmol/L | <10.0 – 8.0 g/dL <100 – 80 g/L <6.2 – 4.9 mmol/L | <8.0 g/dL <80 g/L <4.9 mmol/L; transfusion indicated | life-threatening consequences; urgent intervention indicated |
| Leukocytes (total white blood cell) | <3.40 – 3.0×10 ⁹ /L <3.40 10 ³ /uL – 3000/mm ³ (ULN=10.80 10 ³ /μL) | <3.0 – 2.0×10 ⁹ /L <3000 – 2000/mm ³ | <2.0 – 1.0×10 ⁹ /L <2000 – 1000/mm ³ | <1.0×10 ⁹ /L <1000/mm ³ |
| Lymphocytes | not applicable | <700 – 500/mm ³ <0.7 – 0.5×10 ⁹ /L | <500 – 200/mm ³ <0.5 – 0.2×10 ⁹ /L | <200/mm ³ <0.2×10 ⁹ /L |
| Neutrophils | not applicable | <1.4 – 1.0×10 ⁹ /L <1400 – 1000/mm ³ | <1.0 – 0.5×10 ⁹ /L <1000 – 500/mm ³ | <0.5×10 ⁹ /L <500/mm ³ |
| Platelets | <155 – 75.0×10 ⁹ /L <155 10 ³ /uL – 75,000/mm ³ (ULN=379 10 ³ /μL) | <75.0 – 50.0×10 ⁹ /L <75,000 – 50,000/mm ³ | <50.0 – 25.0×10 ⁹ /L <50,000 – 25,000/mm ³ | <25.0×10 ⁹ /L <25,000/mm ³ |
| METABOLIC/LABORATORY | | | | |
| Albumin, serum- low (hypoalbuminemia) | 2 - 59 years (ULN=5.5 g/dL) <3.5 – 3 g/dL <35 – 30 g/L 59 -69 years (LLN-ULN) <3.6 g/dL – 3 g/dL 69 -79 years (LLN-ULN) <3.5 g/dL – 3g/dL 79 -89 years (LLN-ULN) <3.5g/dL – 3g/dL | <3 – 2 g/dL <30 – 20 g/L | <2 g/dL <20 g/L | life-threatening consequences; urgent intervention indicated |
| Alkaline phosphatase | Female: 18 -19 years >101 – 3.0×101 19 -61 years ULN=107 61 -71 years ULN=112 71 -150 years ULN=108 Male 18 -19 years >127 – 3.0×127 19 -61 years ULN=102 61 -71 years ULN=103 71 -150 years ULN=105 | >3.0 – 5.0×ULN See previous column for ULN values | >5.0 – 20.0×ULN See previous column for ULN values | >20.0×ULN See previous column for ULN values |
| Alanine aminotransferase | Female: >32 – 3.0×32 | Female: >3.0 – 5.0×32 | Female: >5.0 – 20.0×32 | Female: >20.0×32 |

| | Grade 1 | Grade 2 | Grade 3 | Grade 4 |
|---|--|--|---|---|
| | Male: >44 – 3.0 x 44 | Male >3.0 – 5.0x44 | Male: >5.0 – 20.0x44 | Male: >20.0x44 |
| Aspartate aminotransferase | >40 – 3.0x40 | >3.0 – 5.0x40 | >5.0 – 20.0x40 | >20.0x40 |
| Bilirubin (hyperbilirubinemia) | >1.2 – 1.5x1.2 | >1.5 – 3.0x1.2 | >3.0 – 10.0x1.2 | >10.0x1.2 |
| Calcium, serum-low (hypocalcemia) (conversion to mmolx0.25) | <8.5 – 8.0 mg/dL <2.13 – 2.0 mmol/L | <8.0 – 7.0 mg/dL <2.0 – 1.75 mmol/L | <7.0 – 6.0 mg/dL <1.75 – 1.5 mmol/L | <6.0 mg/dL <1.5 mmol/L |
| Calcium, serum-high (hypercalcemia) | >10.6 – 11.5 mg/dL >2.65 – 2.9 mmol/L | >11.5 – 12.5 mg/dL >2.9 – 3.1 mmol/L | >12.5 – 13.5 mg/dL >3.1 – 3.4 mmol/L | >13.5 mg/dL >3.4 mmol/L |
| Cholesterol, serum-high (hypercholesterolemia) (conversion to mmol/L x0.02586) | 0 -19 years >169 – 300 mg/dL >4.37 – 7.75 mmol/L 19 -150 years >199 – 300 mg/dL >5.15 – 7.75 mmol/L | >300 – 400 mg/dL >7.75 – 10.34 mmol/L | >400 – 500 mg/dL >10.34 – 12.92 mmol/L | >500 mg/dL >12.92 mmol/L |
| Creatinine | Female >1.00 mg/dL – 1.5x1.00 Male >1.27 mg/dL – 1.5x1.27 | Female >1.5 – 3.0x1.00 Male >1.5 mg/dL – 3.0x1.27 | Female >3.0 – 6.0x1.00 Male >3.0 mg/dL – 6.0 x1.27 | Female >6.0x1.00 Male >6.0x1.27 |
| Gamma glutamyl transpeptidase | Female >60 IU/L – 3.0x60 Male >65 IU/L – 3.0x65 | Female >3.0 – 5.0x60 Male >3.0 – 5.0x65 | Female >5.0 – 20.0x60 Male >5.0 – 20.0x65 | Female >20.0x60 Male >20.0x65 |
| Glucose, serum-high (hyperglycemia) (conversion to mmol/L x0.0555) | Fasting glucose value >99 – 160 mg/dL >5.5 – 8.9 mmol/L | Fasting glucose value >160 – 250 mg/dL >8.9 – 13.9 mmol/L | >250 – 500 mg/dL; >13.9 – 27.8 mmol/L; hospitalization indicated | >500 mg/dL; >27.8 mmol/L; life-threatening consequences |
| Glucose, serum-low (hypoglycemia) | <65 – 55 mg/dL <3.6 – 3.0 mmol/L | <55 – 40 mg/dL <3.0 – 2.2 mmol/L | <40 – 30 mg/dL <2.2 – 1.7 mmol/L | <30 mg/dL <1.7 mmol/L life-threatening consequences; seizures |
| Phosphate, serum-low (hypophosphatemia) (conversion to mmol/L x0.323) | not applicable | <2.5 – 2.0 mg/dL <0.8 – 0.6 mmol/L | <2.0 – 1.0 mg/dL <0.6 – 0.3 mmol/L | <1.0 mg/dL <0.3 mmol/L life-threatening consequences |
| Potassium, serum-high (hyperkalemia) | not applicable | >5.5 – 6.0 mmol/L | >6.0 – 7.0 mmol/L hospitalization indicated | >7.0 mmol/L life-threatening consequences |
| Potassium, serum-low (hypokalemia) | <3.5 mEq/L – 3.0 mmol/L | <LLN – 3.0 mmol/L; symptomatic; intervention indicated | <3.0 – 2.5 mmol/L hospitalization indicated | <2.5 mmol/L life-threatening consequences |
| Sodium, serum-high (hypernatremia) | >144 mEq/L – 150 mmol/L | >150 – 155 mmol/L | >155 – 160 mmol/L hospitalization indicated | >160 mmol/L life-threatening consequences |
| Sodium, serum-low (hyponatremia) | <134 mEq/L – 130 mmol/L | Not applicable | <130 – 120 mmol/L | <120 mmol/L life-threatening consequences |
| Triglyceride, serum-high (hypertriglyceridemia) | 150 – 300 mg/dL 1.71 – 3.42 mmol/L | >300 – 500 mg/dL >3.42 – 5.7 mmol/L | >500 – 1000 mg/dL >5.7 – 11.4 mmol/L | >1000 mg/dL >11.4 mmol/L life-threatening consequences |

| | Grade 1 | Grade 2 | Grade 3 | Grade 4 |
|--|---|----------------|---|---|
| Uric acid, serum-high (hyperuricemia) | Female >7.1 – 10 mg/dL Male >8.6 – 10 mg/dL Both ≤0.59 mmol/L without physiologic consequences | Not applicable | Female >7.1 – 10 mg/dL Male >8.6 – 10 mg/dL Both ≤0.59 mmol/L without physiologic consequences | >10 mg/dL >0.59 mmol/L life-threatening consequences |

LLN = lower limit of normal, ULN = upper limit of normal.

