9.7.1.1 Study Endpoints

9.7.1.1.1 PRIMARY ENDPOINT

- Safety and tolerability, which include incidence of TEAEs and SAEs, laboratory parameters, vital signs, and ECG parameters (revised per Amendment 05)

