9.7.1.8.3 LABORATORY VALUES

Laboratory results will be summarized using International System of Units, as appropriate. For all quantitative parameters listed in [Section 9.5.1.5.3](#), the actual value and the change from baseline to each postbaseline visit and to the end of treatment (defined as the last on-treatment value) will be summarized by visit and treatment group using descriptive statistics. Qualitative parameters listed in [Section 9.5.1.5.3](#) will be summarized using frequencies (number and percentage of subjects), and changes from baseline to each postbaseline visit and to end of treatment will be reported using shift tables. Percentages will be based on the number of subjects with both nonmissing baseline and relevant postbaseline results.

Laboratory test results will be assigned a low/normal/high (LNH) classification according to whether the value was below (L), within (N), or above (H) the laboratory parameter's reference range. Within-treatment comparisons for each laboratory parameter will be based on 3-by-3 tables (shift tables) that compare the baseline LNH classification to the LNH classification at each postbaseline visit and at the end of treatment. Similar shift tables will also compare the baseline LNH classification to the LNH classification for the highest and lowest value during the treatment period.

[Appendix 1](#) (Sponsor's Grading for Laboratory Values) presents the criteria that will be used to identify subjects with treatment-emergent markedly abnormal laboratory values (TEMAVs). Except for phosphate, a TEMAV is defined as a postbaseline value with an increase from baseline to a Grade of 2 or higher. For phosphate, a TEMAV was defined as a postbaseline value with an increase from baseline to a Grade of 3 or higher. When displaying the incidence of TEMAVs, each subject may be counted once in the laboratory parameter high and in the laboratory parameter low categories, as applicable.

Lymphocyte subsets measured (including but not limited to CD4 [T helper cells], CD8 [cytotoxic T cells], CD19 [B cells], CD16/CD56 [natural killer cells] and CD14 [macrophages] and regulatory T cells) will be summarized in the same manner as other laboratory parameters. Mean lymphocyte subsets and the mean change from baseline in lymphocyte subsets will also be displayed graphically over time by dose.

Serum IgG, IgM, and IgA will be measured and summarized in the same manner as other laboratory parameters.

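### Two rows of Appendix 1 (male creatinine and uric acid) give one value two grades on opposite sides of the cut-off for a markedly abnormal laboratory value

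*Protocol*

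**What the plan says.** Protocol section 9.7.1.8.3 names Appendix 1 as the source of the TEMAV criteria and sets the rule: "Except for phosphate, a TEMAV is defined as a postbaseline value with an increase from baseline to a Grade of 2 or higher". Phosphate alone has a different cut, Grade 3 or higher.

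In Appendix 1 the creatinine row for men reads:

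- Grade 1: "Male >1.27 mg/dL – 1.5x1.27"
- Grade 2, with the female cell before it: "Female >1.5 – 3.0x1.00 Male >1.5 mg/dL – 3.0x1.27"
- Grade 3: "Male >3.0 mg/dL – 6.0 x1.27"
- Grade 4: above 6.0 × 1.27, with no unit

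The uric acid row, from the end of its Grade 1 cell through Grades 2 and 3, reads "without physiologic consequences | Not applicable | Female >7.1 – 10 mg/dL Male >8.6 – 10 mg/dL Both ≤0.59 mmol/L without physiologic consequences" (the bars separate the columns). The Grade 1 cell carries the same limits and the same closing words as the Grade 3 cell. Grade 4 is above 10 mg/dL.

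Laboratory results belong to the primary endpoint in section 9.7.1.1.1: "Safety and tolerability, which include incidence of TEAEs and SAEs, laboratory parameters, vital signs, and ECG parameters". TEMAVs are not named there.

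**The concern.** A TEMAV depends entirely on which side of the Grade 1 / Grade 2 line a value falls. If one value satisfies both a Grade 1 cell and a higher-grade cell, the table does not say whether the subject counts. A programmer must choose, and two programmers following the same text can produce different TEMAV tables from the same data. The protocol itself fixes both the rule and the cut-points, so this is not detail left open for the analysis plan. No tie-break appears in the protocol text available.

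At stake is the TEMAV incidence by treatment group for two analytes. Taking the lower grade drops the doubtful values. Taking the higher grade reports a male creatinine only slightly above normal, or any raised uric acid, as markedly abnormal.

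**Working it through.** The plan states no figure to reproduce. The check is to evaluate the cut-points in Appendix 1 and intersect the grade intervals.

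**Inputs (Appendix 1).** Male creatinine limit 1.27 mg/dL, multipliers 1.5, 3.0 and 6.0. Female creatinine limit 1.00 mg/dL, same multipliers. Uric acid above 7.1 (female) or 8.6 (male) up to 10 mg/dL. TEMAV cut: Grade 2 (section 9.7.1.8.3).

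**Male creatinine as written**

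- Grade 1: above 1.27 to 1.5 × 1.27 = 1.905 mg/dL
- Grade 2: above 1.5 to 3.0 × 1.27 = 3.81 mg/dL
- Grade 3: above 3.0 to 6.0 × 1.27 = 7.62 mg/dL
- Grade 1/2 overlap: above 1.5 to 1.905 mg/dL. Share of the Grade 1 interval: (1.905 − 1.5) / (1.905 − 1.27) = 0.405 / 0.635 = 64%
- Grade 2/3 overlap: above 3.0 to 3.81 mg/dL

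The Grade 1/2 overlap starts at 1.5 / 1.27 = 1.18 times the limit. A man who goes from normal to 1.6 mg/dL (1.6 / 1.27 = 1.26 times the limit) is Grade 1, no TEMAV, and also Grade 2, a TEMAV. A man who goes from normal to 3.5 mg/dL is Grade 2 and Grade 3, but is a TEMAV either way.

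**Male creatinine with every bound read as a multiple of 1.27.** Grade 1 above 1.27 to 1.905, Grade 2 above 1.905 to 3.81, Grade 3 above 3.81 to 7.62, Grade 4 above 7.62 mg/dL. There is no overlap and no gap. Female creatinine is contiguous on either reading because its limit is 1.00. The ALT, AST, bilirubin and GGT rows give the lower multiple without a unit.

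**Uric acid.** Grade 1 and Grade 3 are the same set: above 7.1 to 10 mg/dL in women, above 8.6 to 10 mg/dL in men. Grade 2 is marked as not applicable. A woman who goes from normal to 9 mg/dL is Grade 1, no TEMAV, and Grade 3, a TEMAV. Read as Grade 1, uric acid TEMAVs start only above 10 mg/dL. Read as Grade 3, they start immediately above normal. Nothing in the row separates the two readings.

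The other version of Appendix 1 in the protocol file has the same cells, so this is not an artefact of text extraction.

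**The case against.** The best reply on creatinine is that the table resolves its own slip. Only the multiple-of-limit reading makes the grades contiguous, the neighbouring rows follow it, and the unit in the male Grade 2 and Grade 3 cells looks carried over from Grade 1. That is probably right about the intent, and it is why the correction is easy to specify. It does not make the text correct: followed literally, it gives a different count. No such argument is available for uric acid.

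The rest of the reply limits the reach of the point, and it stands:

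- A reader might add low potassium, where Grades 1 and 2 share a numeric range. But Grade 2 is "<LLN – 3.0 mmol/L; symptomatic; intervention indicated", so a clinical qualifier separates the grades. How to combine it with the laboratory value is a derivation detail, not a contradiction.
- A reader might infer that abnormal values would be hidden. Section 9.7.1.8.3 also requires low/normal/high shift tables, including for the highest and lowest on-treatment value, and summaries of actual values and changes. None of these uses Appendix 1 grades, so a raised creatinine or uric acid still appears as high.
- A reader might call this a defect in the primary analysis. The primary endpoint names laboratory parameters, not TEMAVs. TEMAV incidence is descriptive, and no test, decision rule or sample size rests on it.
- The creatinine Grade 2/3 overlap does not change TEMAV status from a baseline below Grade 2.

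**Conclusion.** The point holds for two rows. Male creatinine above 1.5 to 1.905 mg/dL (64% of the Grade 1 interval) is double-graded 1 and 2. All uric acid values above normal up to 10 mg/dL are double-graded 1 and 3. Both straddle the TEMAV cut, so TEMAV status is undefined for a subject who moves into either band from a normal baseline.

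The consequence is confined to one descriptive table. The documents do not show how many subjects will fall in these bands. With about 15 per arm, each such subject moves an arm's incidence by 1/15 = 6.7 percentage points. With 60 ± 20% randomized, that is 12 to 18 per arm, or 8.3 to 5.6 points. This is true of any count in a trial of this size and is not an estimate of the error.

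The conclusion assumes that no tie-break exists elsewhere. The statistical analysis plan was not available for this check. The protocol does not show which of the two uric acid cells is wrong, so it supports no particular replacement threshold for that analyte.

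**What to change.** 1. **Male creatinine.** Write Grade 2 as >1.5 × 1.27 to 3.0 × 1.27 and Grade 3 as >3.0 × 1.27 to 6.0 × 1.27, in line with the table's other rows. This removes both overlaps.
2. **Uric acid.** Reconcile the Grade 1 and Grade 3 cells with the grading used by the central laboratory before TEMAV tables are programmed. The revision history for Amendment 01 gives alignment with that laboratory as the reason for its corrections to Appendix 1; creatinine was among the analytes revised, uric acid was not.
3. **If the uric acid grades differ only by a clinical qualifier** that laboratory data do not hold, state in section 9.7.1.8.3 which grade is counted from the value alone. The separate phosphate threshold is a precedent.

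The cost is a few table cells and at most one sentence. No data collection, visit or sample size changes.

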Appendix 2 List of Permitted and Prohibited Prior/Concomitant Medications

Prohibited medications are shown in [Listing 1](#) through [Listing 5](#). Medications permitted with restrictions are listed in [Listing 6 through Listing 8](#). (revised per Amendment 04) **These may not be all-inclusive listings.** Please contact the medical monitor(s) if the investigators have any questions or concerns regarding any medication not listed that your subjects may be taking before enrollment or start during the course of the E2609-G000-202 study.

Antibiotics, analgesics, and anti-inflammatory drugs intended for short courses of treatment are permitted and do not need to follow the restrictions of [Listing 8](#) for a stable dose of 4 weeks before Baseline. If these medications may affect cognitive function but the medications are clinically indicated, then cognitive testing should not take place until at least 72 hours after the last dose of the course of treatment.

Prohibited Prior/Concomitant Medications

Listing 1 Drugs with High Risk of Torsades de Pointes or QTc Prolongation

| Generic name | Brand name (Names shown are not exhaustive and are examples only; names may be the ® or ™) | Comments |
|---|--|---|
| Prohibited from 14 days (or 5 half-lives, whichever is longer) before Randomization until after the last treatment visit | | |
| Anti-arrhythmic/ abnormal heart rhythm | | |
| Amiodarone | Cordarone; Pacerone | Incidence in females greater than males, Torsades de Pointes risk regarded as low |
| Disopyramide | Norpace | Incidence in females greater than males |
| Dofetilide | Tikosyn | |
| Ibutilide | Corvert | Incidence in females greater than males |
| Procainamide | Pronestyl; Procan | |
| Quinidine | Cardioquin; Quinaglute | Incidence in females greater than males |
| Sotalol | Betapace | Incidence in females greater than males |
| Antihistamine/ allergic rhinitis | | |
| Astemizole | Hismanal | No longer available in United States |
| Terfenadine | Seldane | No longer available in United States |
| Anti-anginal/ heart pain | | |
| Bepridil | Vascor | Incidence in females greater than males |
| Antibiotic/ bacterial infection | | |
| Clarithromycin | Biaxin | |
| Moxifloxacin | Avelox | |
| Sparfloxacin | Zagam | |
| Listing 1 continued | | |
| Antimalarial/ malaria infection | | |
| Chloroquine | Aralen | |
| Halofantrine | Halfan | Incidence in females greater than males |
| Antipsychotic/ anti-emetic/ schizophrenia/ nausea | | |
| Chlorpromazine | Thorazine | |
| Gastrointestinal stimulant/ heartburn | | |
| Cisapride | Propulsid | |

Listing 1 Drugs with High Risk of Torsades de Pointes or QTc Prolongation

| Generic name | Brand name (Names shown are not exhaustive and are examples only; names may be the ® or ™) | Comments |
|--|--|---|
| Antinausea/ nausea | | |
| Domperidone | Motillum | Not available in the United States |
| Sedative; antinausea/ anesthesia adjunct, nausea | | |
| Droperidol | Inapsine | |
| Antibiotic; gastrointestinal stimulant/ bacterial infection; increase gastrointestinal motility | | |
| Erythromycin | Erythrocin; E.E.S. | Incidence in females greater than males |
| Antipsychotic/ schizophrenia | | |
| Haloperidol | Haldol | When given intravenously or at higher than recommended doses, risk of sudden death, QT prolongation, and torsades increases |
| Mesoridazine | Serentil | |
| Thioridazine | Mellaril | |
| Opiate agonist/ pain control, narcotic dependence | | |
| Levomethadyl | Orlaam | |
| Methadone | Methadose; Dolophine | Incidence in females greater than males |
| Anti-infective/ pneumocystis pneumonia | | |
| Pentamidine | Pentam; NebuPent | Incidence in females greater than males |
| Antipsychotic/ Tourette's ties | | |
| Pimozide | Orap | Incidence in females greater than males |
| Antilipemic/ hypercholesterolemia | | |
| Probucol | Lorelco | No longer available in United States |
| Anticancer | | |
| Arsenic trioxide | Trisenox | Used for leukemia |
| Vandetanib | Zactima | Used for thyroid cancer |

Note: This list is not exhaustive.

QTc = Corrected QT interval.

Listing 2 Prohibited Medications Within 5 Half-lives or 60 days, Whichever is Longer, Before Randomization and Until after the Last Treatment Visit

| Generic name | Brand name (Names shown are not exhaustive and are examples only; names may be the ® or ™) |
|---|--|
| Systemic Immunosuppressants^{a,b} and Immunomodulatory therapy | |
| Azathioprine | Azasan, Imur |
| Ciclosporine | Gengraf, Neoral |
| Dexamethasone | Decadron, Dexasone, Diodex, Hexadrol, Maxidex |
| Fingolimod | Gilenya |
| Methotrexate | Trexall |
| Methylprednisolone | Medrol, Meprolone |
| Mycophenolate | CellCept, Myfortic |
| Prednisolone | Deltasone, Prednicot, Prednisone Intensol, Rayos, Sterapred, Sterapred DS |

Note: This list is not exhaustive.

- a: Topical and inhaled formulations with minimal systemic exposure need not be prohibited.
- b: During the treatment period of the study, short term (not more than 14 days) use of steroids up to the equivalent of prednisolone 40 mg OD is permitted after discussion with the Medical Monitor. Dosing with study drug should be suspended from the time steroid treatment is started. Complete blood count and lymphocyte subsets should be determined prior to starting steroid treatment and continue to be monitored weekly. Study drug may be resumed after discussion with the Medical Monitor when the following conditions are met: (1) treatment with steroids has been completed for at least 1 week; (2) total lymphocytes not <LLN; (3) no lymphocyte subsets are below the discontinuation threshold; (4) the investigator considers that the medical condition which required treatment with steroids has improved or resolved. Weekly testing of lymphocyte subset counts and CBC with differentials is required for 4 weeks following resumption of study drug administration. (revised per Amendment 04)

Listing 3 Prohibited Medications Within 6 Months Before Randomization

| Generic name | Brand name (Names shown are not exhaustive and are examples only; names may be the [®] or [™]) |
|---|---|
| Immunoglobulin therapy | |
| Adalimumab | Humira |
| Bevacizumab | Avastin |
| Efalizumab | Raptiva |
| Etanercept | Enbrel |
| Immune globulin IV, IVIG, IGIV | Carimune, Flebogamma, Gamimune N, Gammagard, Gamunex, Gammar-P IV, Iveegam, Octagam, Panglobulin, Vigam, Polygam S/D, Privigen, Sandoglobulin, Venoglobulin-S |
| Infliximab | Remicade |
| Omalizumab | Xolair |
| Ranibizumab | Lucentis |
| Other monoclonal antibodies not listed here | |

Note: This list is not exhaustive.

Listing 4 Prohibited Live Vaccines Within 3 Months Before Randomization Until after the Last Treatment Visit (this does not apply to non-live/inactivated vaccines)

| Bacterial vaccines | Viral vaccines |
|---|---|
| Bacillus Calmette-Guérin vaccine against tuberculosis | Measles vaccination |
| Cholera vaccination (oral) | Rubella vaccination |
| | Oral polio vaccination (Sabin) |
| | Yellow fever vaccination |
| | Varicella (chickenpox) vaccination |
| | Rotavirus vaccination |
| | Japanese encephalitis vaccination |
| | Live attenuated influenza vaccine (FluMist, Fluenz) |
| Typhoid vaccination (oral) | Mumps vaccination |

Note: This list is not exhaustive

Listing 5 Strong CYP3A4 Inhibitors Prohibited Within 5 Half-Lives or 14 Days (Whichever Is Longer) Before Randomization Until After the Last Treatment Visit

| Generic name | Brand name(s) |
|----------------|--|
| boceprevir | Victrelis |
| clarithromycin | Clarithromycin, clarithromycin extended release, Prevpac |
| cobicistat | Tybost, Stribild, |
| conivaptan | Vaprisol |
| danoprevir | |
| elvitegravir | Vitekta, Stribild |
| indinavir | Crixivan |
| itraconazole | Sporanox, Onmel |
| ketoconazole | Xolegel, Nizoral, Ketodan |
| lopinavir | Kaletra |
| nefazodone | Serzone |
| nelfinavir | Viracept |
| posaconazole | Noxafil |
| ritonavir | Norvir, Kaletra |
| saquinavir | Invirase, Fortovase |
| telaprevir | Incivek |
| telithromycin | Ketek |
| tipranavir | Aptivus |
| troleandomycin | Triocetin |
| voriconazole | Vfend, Voriconazole |

Note: This list is not exhaustive

Permitted Prior/Concomitant Medications

Listing 6 Medications Which Need To Be on a Stable Dose for 12 Weeks Before the Baseline Cognitive Assessments at Visit 2 and Remain on the Same Stable Dose from Baseline to Final Follow-Up Visit

| Generic name | Brand name (Names shown are not exhaustive and are examples only; names may be the ® or ™) |
|----------------------------|--|
| Cognitive Enhancers | |
| Donepezil | Aricept |
| Galantamine | Reminyl |
| Memantine | Namenda |
| Rivastigmine | Exelon |

Note: This list is not exhaustive.

Listing 7 Permitted Medications Used on PRN Basis Which are Not to be Used Within 72 Hours before Cognitive Testing

| Generic name | Brand name (Names shown are not exhaustive and are examples only; names may be the ® or ™) |
|---|---|
| Opiates | |
| Morphine | Astramorph PF, Avinza, Depo Dur, Duramorph, Infumorph, Kadian, MS Contin, MSIR, Oramorph SR, RMS, Roxanol |
| Opiate Agonists | |
| Codeine | Codeine |
| Fentanyl | Actiq, Duragesic, Fentora, Onsolis, Sublimaze |
| Meperidine | Demerol, Meperitab |
| Oxycodone | Dazidox, Endocodone, Eth-OxyDose, OxyContin, OxyFast, OxyIR, Percolone, Roxicodone, Roxicodone Intensol |
| Other opioids or opioid agonists which are used on PRN basis | |
| Benzodiazepines and sedatives | |
| Alprazolam | Alprazolam Intensol, Niravam, Xanax |
| Amitriptyline | (various) |
| Chlordiazepoxide | H-Tran, Librium |
| Clonazepam | Ceberclon, Klonopin |
| Diazepam | Diastat, Dizac, Valium |
| Dothiepin | (various) |
| Estazolam | ProSom |
| Flunitrazepam | Rohypnol |
| Flurazepam | Dalmane |
| Lorazepam | Ativan |
| Midazolam | Versed |
| Olanzapine | Zyprexa |
| Promethazine | Phenergan; others |
| Ramelteon | Rozerem |
| Risperidone | Risperdal |
| Temazepam | Restoril |
| Triazolam | Halcion |
| Zolpidem | Ambien; others |
| Zopiclone | (various) |
| Other benzodiazepines, tricyclic antidepressants, antipsychotics and other drugs which are used on PRN basis as sedatives | |

Note: This list is not exhaustive

**Listing 7 Permitted Medications Used on PRN Basis Which are Not to be Used
Within 72 Hours before Cognitive Testing**

| Generic name | Brand name (Names shown are not exhaustive and are examples only; names may be the [®] or [™]) |
|--------------|--|
|--------------|--|

PRN = Pro re nata

Listing 8 Permitted Centrally Active or Psychiatric Medications

| Generic Name | Brand name (Names shown are not exhaustive and are examples only; names may be the ® or ™) |
|--|--|
| 
If to be used on a PRN basis see Listing 7. If to be used chronically, subjects must be on a stable dose for ≥4 weeks before Baseline. Changes in dose or initiation of new concomitant medications for chronic use (not PRN use) is permitted but if the medication affects cognitive function, do not conduct cognitive testing until the dose is stable for 4 weeks.
 | |
| Antidepressants | |
| Amitriptyline hydrochloride | Elavil |
| Amoxapine | Amoxapine |
| Bupropion | Aplenzin, Budeprion, Buproban, Zyban, Wellbutrin |
| Citalopram | Celexa |
| Clomipramine hydrochloride | Anafranil |
| Desipramine hydrochloride | Norpramin |
| Desvenlafaxine | Pristiq |
| Doxepin hydrochloride | Prudoxin, Silenor, Sinequan, Zonalon |
| Duloxetine | Cymbalta |
| Escitalopram | Lexapro |
| Fluoxetine | Prozac, Sarafem, Selfemra |
| Fluvoxamine | Luvox |
| Imipramine hydrochloride | Tofranil |
| Isocarboxazid | Marplan |
| Maprotiline hydrochloride | Ludiomil |
| Mirtazapine | Remeron Soltab |
| Nortriptyline hydrochloride | Aventyl, Pamelor |
| Paroxetine | Paxil, Pexeva |
| Phenelzine | Nardil |
| Protriptyline hydrochloride | Vivactil |
| Rasagiline | Azilect |
| Selegiline | EMSAM |
| Sertraline | Sertaraline, Zoloft |
| Tranlycypromine | Parnate |
| Trazodone hydrochloride | Desyrel, Oleptro |
| Trimipramine maleate | Surmontil |
| Venlafaxine hydrochloride | Effexor |

Listing 8 Permitted Centrally Active or Psychiatric Medications

| Generic Name | Brand name (Names shown are not exhaustive and are examples only; names may be the ® or ™) |
|---|--|
| Mood Stabilizers (Listing 8 continued) | |
| Carbamazepine | Carbatrol, Epitol, Equetro, Tegretol, Tegretol XR |
| Lamotrigine | Lamictal, Lamictal CD, Lamictal ODT, Lamictal XR |
| Valproic acid | Depacon, Depakene, Depakote, Depakote ER, Divalproex Sodium, Stavzor, Valproate |
| Antipsychotics | |
| Acetophenazine | Tindal |
| Aripiprazole | Abilify |
| Asenapine | Saphris |
| Olanzapine | Zyprexa |
| Chlorpromazine | Thorazine |
| Haloperidol | Haloperidol, Haldol |
| Clozapine | Clozaril, Fazacllo |
| Fluphenazine | Prolixin |
| L-Methylfolate | Deplin, L-Methylfolate Calcium |
| Loxapine | Loxitane |
| Mesoridazine | Serentil |
| Perphenazine | Trilafon |
| Quetiapine | Seroquel |
| Risperidone | Risperdal |
| Thioridazine | Mellaril |
| Thiothixene | Navane |
| Trifluoperazine | Stelazine |
| Benzodiazepines | |
| Alprazolam | Alprazolam Intensol, Niravam, Xanax |
| Chlordiazepoxide | H-Tran, Librium |
| Clonazepam | Ceberclon, Klonopin |
| Diazepam | Diastat, Dizac, Valium |
| Estazolam | ProSom |

Listing 8 Permitted Centrally Active or Psychiatric Medications

| Generic Name | Brand name (Names shown are not exhaustive and are examples only; names may be the ® or ™) |
|---------------|--|
| Flunitrazepam | Rohypnol |
| Flurazepam | Dalmane |
| Lorazepam | Ativan |
| Midazolam | Versed |
| Temazepam | Restoril |
| Triazolam | Halcion |
| Zopiclone | Imovane, Zimovane |
| Zopidem | Ambien, Ambien CR, Intermezzo, Stilnox, Stilnoct, Sublinox, Hypnogen, Zolsana |

Note: This list is not exhaustive.

PRN = Pro re nata

